#### **BEGINNODATA;**

```
array gammac[5];
  array gammat[5];
  array pc[5];
  array pt[5];
  DO i = 1 to 5;
   gammac[i] = logistic(theta[i] + beta0 + 0.5*beta3);
   gammat[i] = logistic(theta[i] + beta0 + beta1 + 0.5*beta3);
  END;
 pc1 = gammac1;
 pc2 = gammac2 - gammac1;
 pc3 = gammac3 - gammac2;
 pc4 = gammac4 - gammac3;
 pc5 = 1 - sum(of pc1-pc4);
 pt1 = gammat1;
 pt2 = gammat2 - gammat1;
 pt3 = gammat3 - gammat2;
 pt4 = gammat4 - gammat3;
 pt5 = 1 - sum(of pt1-pt4);
 p2box c = pc1 + pc2;
 p2box t = pt1 + pt2;
 diff = p2box t - p2box c;
ENDNODATA:
RUN;
```

# Where,

ads\_VS =analysis data set for Vision Satisfaction in Bright Lighting trtan= numerical representation of treatment, where Test=1 and Control=0

```
CR-6305, Statistical Analysis Plan Version 1.0
```

age= Age of subject at time of consent sexn= Numerical representation of sex, where Female=1 and Male=0; siteid= Site Number

Lens Fit

```
PROC MCMC DATA=ads_LF DIC MCHISTORY=brief

NBI=50000 NMC=200000 THIN = 50 STATS=ALL plots(smooth) MONITOR=(_parms_)

OUTPOST =post STATS(ALPHA=(0.05) PERCENTAGE=(2.5 25 50 75 97.5) ) SEED=53457 ;

ODS OUTPUT PostSummaries = PostSummaries ;

ODS OUTPUT PostIntervals = PostIntervals ;

BY trta;

PARM p 0.5 ;

PARM ro .6 ;

PRIOR ro ~uniform(0,1);

PRIOR p ~ beta(0.5, 0.5);

;

llike = log( (1-ro)*PDF('BINOMIAL', y, p, 2) + z*ro*(PDF('BINOMIAL',y,p,2)**0.5));

MODEL y ~ GENERAL(llike);

RUN;

Slit lamp Findings (Grade 3 or higher)
```

```
PROC MCMC DATA=ads SLF DIC MCHISTORY=brief

NBI=100000 NMC=500000 THIN =100 STATS=ALL plots(smooth) MONITOR=(_parms_

P C P T)

OUTPOST =post STATS(ALPHA=(0.05) PERCENTAGE=(2.5 25 50 75 97.5)) SEED=53457 ;

ODS OUTPUT PostSummaries = PostSummaries ;

ODS OUTPUT PostIntervals = PostIntervals ;

PARMS (beta0 beta1 beta2 beta3) 0 sigma_site 1 sigma_subject 1;

PRIOR beta: ~NORMAL(0, var=1000);

PRIOR sigma_site~ IGAMMA(shape=0.01, scale=0.01);

PRIOR sigma_subject ~UNIFORM(0,100);
```

```
RANDOM gamma site ~NORMAL(0, var=sigma site) SUBJECT=siteid;
RANDOM gamma_subject ~NORMAL(0, sd=sigma_subject) SUBJECT=site_subjid;
```

 $mu = beta0 + beta1*trtan + beta2*age + beta3*sexn + gamma_site + gamma_subject;$ 

p = logistic(mu);

MODEL  $y \sim BINARY(P);$ 

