#### **Slit Lamp Findings**

Grade 3 or higher slit lamp findings will be analyzed using a Bayesian Logistic regression random-effects model to compare the Test and Control lenses. The regression model will include baseline slit lamp findings and lens type. Site and subject will be included in the model as random effects.

Let  $y_{ijkl}=1$  if a Grade 3 or higher SLF is observed and  $y_{ijkl}=0$  otherwise for the  $l^{th}$  subject, from the  $k^{th}$  site, assigned to the  $i^{th}$  study lens for the  $j^{th}$  eye.

yijkl ~ Binary (pijkl)

$$p_{ijkl} = \frac{\exp(\beta_0 + \beta_1 Lens_i + \beta_2 Baseline SLF_1 + \gamma_k + \delta_l)}{1 + \exp(\beta_0 + \beta_1 Lens_i + \beta_2 Baseline SLF_1 + \gamma_k + \delta_l)}$$

We assume the random effect for subject are i.i.d as  $\delta_{l} \sim N(0, \sigma_{subject}^{2})$  for the random for clinical site are i.i.d as  $\gamma_{k} \sim N(0, \sigma_{site}^{2})$  for i=1,2 (lens), j=1, 2 (eye), k=1, 2, 3, 4, 5, 6 (site) and l=1,...n (subject/site).

In this model, we define  $Lens_i=0$  for the Control lens and  $Lens_i=1$  for the Test lens. For the  $\beta$  coefficients, independent non-informative priors N(0,1000) will be used. For the variance of random effects of  $\sigma_{subject}^2$  and  $\sigma_{site}^2$ , independent non-informative conjugate priors inverse-gamma (0.001, 0.001) will be used. The Metropolis-Hastings algorithm as implemented in the SAS/STAT 14.2 PROC MCMC procedure will be used to estimate posterior distributions of the unknown parameters. Inferences will be made based on the posterior credible interval for the relevant parameters.

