Vision Satisfaction in Bright Lighting

```
PROC MCMC DATA =ads VS SEED=20181019 nbi =100000 nmc =500000 thin=100
DIAG=ALL OUTPOST=simout DIC PLOTS(SMOOTH FRINGE) = ALL
MCHISTORY=BRIEF PROPCOV=QUANEW STATS=ALL STATS(ALPHA=(0.05)
PERCENTAGE = (2.5 50 97.5))
plots(smooth)=ALL MONITOR=(_parms_OR);
```

ARRAY theta[4] theta1-theta4; ARRAY gamma[4] gamma1-gamma4;

PARMS theta1-theta4 beta0 0 beta1 0 beta2 0 beta3 0; PARMS s2g 1;

PRIOR beta: ~ NORMAL(0,VAR=1000); PRIOR theta1 ~ NORMAL(0,VAR=100); PRIOR theta2 ~ NORMAL(0,VAR=100,lower=theta1); CR-6305, Statistical Analysis Plan Version 1.0

```
PRIOR theta3 ~ NORMAL(0,VAR=100,lower=theta2);
PRIOR theta4 ~ NORMAL(0,VAR=100,lower=theta3);
PRIOR s2g ~ IGAMMA(.01, s =.01);
```

```
RANDOM Gamma site ~ NORMAL(0, VAR = s2g) SUBJECT=SITEID;

mu = beta0 + beta1*TRTAN + beta2*age + beta3*sexn + Gamma_site;

DO j = 1 to 4;

gamma[j] = logistic(theta[j] + mu);

END;

pi1 = gamma1;

pi2 = gamma2 - gamma1;

pi3 = gamma3 - gamma2;

pi4 = gamma4 - gamma3;

pi5 = 1 - sum(of pi1-pi4);
```

```
llike = logmpdfmultinom(of y1-y5, of pi1-pi5);
MODEL DGENERAL(llike);
```

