### BEGINNODATA;

P C = logistic(beta0 + 0.5\*beta3); P\_T = logistic(beta0 + beta1 + 0.5\*beta3);

Diff = P T - P C; ENDNODATA; run;

Where, ads SLF =analysis data set for Slit Lamp Findings trtan= numerical representation of treatment, where Test=1 and Control=0 age= Age of subject at time of consent sexn= Numerical representation of sex, where Female=1 and Male=0; siteid= Site Number site\_subjid=Unique Subject ID

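### SAP text and SAP code put different priors on the subject effect in the primary slit lamp model, and in borderline data the choice can reverse the non-inferiority decision

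*SAP*

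**What the plan says.** The text of SAP 10.1 (Slit Lamp Findings) fits a logistic model with random site and subject effects. For both variances it says: "independent non-informative conjugate priors inverse-gamma (0.001, 0.001) will be used". Protocol 14.5 gives the same prior for these two variances.

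The slit lamp program in SAP 14.1 differs:

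- Subject: "PRIOR sigma_subject ~UNIFORM(0,100"), used in "RANDOM gamma_subject ~NORMAL(0, sd=sigma_subject) SUBJECT=site_subjid". The uniform prior is therefore on the standard deviation, not the variance.
- Site: "PRIOR sigma_site~ IGAMMA(shape=0.01, scale=0.01"), used as a variance. The scale matches the text but the parameters do not.
- Coefficients: "PRIOR beta: ~NORMAL(0, var=1000"), which agrees with SAP 10.1.

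The program then computes the two rates at the end. The Test rate is "logistic(beta0 + beta1 + 0.5" times the sex coefficient). The Control rate is the same without the lens term. Neither contains a site effect, a subject effect or the age term that the fitted model includes.

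Under SAP 10.1, non-inferiority needs the upper 95% credible limit for the difference in proportions of eyes to lie below 5 points, which means a posterior probability of 0.975. SAP 4.1 requires all five primary hypotheses to be met. SAP section 1 ranks the SAP above the protocol but does not rank SAP text against SAP code.

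**The concern.** Two rules are pre-specified for one must-pass primary safety endpoint. Grade 3+ findings should be rare, so the data say little about the subject variance and the prior largely sets it. If the two priors can fall on opposite sides of 0.975 with the same data, the success criterion is not uniquely defined until someone chooses between text and code. That choice should not remain open once data exist.

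**Working it through.** **The plan's own figure.** The documents give no figure for the effect of the prior. The only slit lamp figure is 80% power in SAP 7.4, from a GEE simulation that uses neither prior. It does not reproduce. With effective eyes per arm 2 × 112 / 1.7 = 131.8, the SE of the log odds ratio is √(2 / (131.8 × 0.05 × 0.95)) = 0.565. Power is then Φ(ln 2 / 0.565 − 1.96) = Φ(−0.73), about 23%. That is a separate matter and has no bearing on the prior.

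**How the priors differ.** Inverse-gamma(0.001, 0.001) on the variance gives a density for the SD σ proportional to σ^(−1.002) exp(−0.001/σ²), which favours small σ. Uniform(0,100) is flat in σ. Relative to the text prior, the code prior gains weight roughly in proportion to σ.

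**Why σ moves Diff.** The population rate is the average of logistic(η + σz) over standard normal z. The code reports logistic(η). Solving for η at fixed population rates:

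| σ | 2% becomes | 7% becomes | coded difference |
|---|---|---|---|
| 0 | 2.0% | 7.0% | 5.0 points |
| 1 | 1.3% | 4.8% | 3.5 points |
| 2 | 0.4% | 1.9% | 1.5 points |

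A larger σ shrinks the coded difference while the proportions of eyes stay the same, so the prior that allows a larger σ is the more lenient.

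**Worked example.** The event counts are assumptions, since the documents hold no trial data. There are 112 per arm (SAP 7.4). Control has 2 one-eye findings, 2/224 = 0.9% of eyes. Test has 8 one-eye and 1 bilateral, 10/224 = 4.5%. The calculation is grid integration over intercept, lens effect and σ, with N(0, 1000) on the coefficients and site, age and sex omitted.

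| Quantity | Text prior | Code prior |
|---|---|---|
| P(Diff < 0.05), random effects at zero | 0.94, fails | 0.99, passes |
| P(Diff < 0.05), averaged over subject effects | 0.81, fails | 0.78, fails |

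A further example adds 10 site effects: 116 per arm, one-eye findings only, 2 Control and 8 Test eyes. With the text's site prior the result is 0.974 (text subject prior) against 0.990 (code subject prior). With the code's site prior it is 0.9745 against 0.990. The subject prior reverses the decision; the site prior barely moves it.

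**How often.** True rates are assumed.

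| Scenario | Text passes | Code passes | Disagree |
|---|---|---|---|
| 2% vs 5%, latent eye correlation 0.3 (112 per arm, 600 trials) | 42% | 61% | 20% |
| Same rates, latent 0.7 (600 trials) | 84% | 95% | 11% |
| 5% vs 5%, binary correlation 0.3 (116 per arm, 1,500 trials) | 95% | 98% | 3% |
| 5% vs 5%, binary correlation 0.70 (1,500 trials) | 100% | 100% | 0% |

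A second run of the first two rows, with 300 trials each, gave 23% and 12%. Across the other rates tried at binary correlation 0.70, disagreement was at most 0.1%. Wherever direction was recorded, the code prior passed and the text prior failed.

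**The case against.** A reader might infer that the prior alone decides this endpoint, or that the two priors routinely give opposite answers. The documents do not support that, for four reasons.

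- **Events may be too few to matter.** The historical studies had no Grade 3+ finding in 860 Test and 270 Control eyes (SAP Table 9), and Grade 2 or worse at baseline is excluded. At true rates of 0.5% or 1% in both arms (latent correlation 0.3), both priors passed all 300 simulated trials. One-eye counts of 0 vs 1, 1 vs 3 and 2 vs 5 also pass under both. Reversal needs a borderline, mostly one-eye excess of about six or more Test eyes, and the exact counts shift with n: 2 vs 8 reverses at 112 and 116 per arm but not at 118.
- **The correlation scale matters.** At rates of 2% to 5%, latent 0.3 is a binary correlation of only about 0.07 to 0.10, and latent 0.7 about 0.30 to 0.36. SAP 7.4 does not say which scale its 0.70 is on. If binary, disagreement nearly vanishes.
- **The example is not the code as written.** The coded Diff omits the age term and is therefore evaluated at age 0. In 40 refits of the same counts, with ages drawn uniformly from 18 to 49, the priors disagreed once; 35 failed and 4 passed under both. Evaluated at mean age, 37 of 40 disagreed.
- **The prior is not the main lever.** Averaging over subject effects gives the same decision under both priors in the example, and cuts disagreement at 2% vs 5% (latent 0.3) from 20% to about 4%.

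All four stand as limits on size. None removes the contradiction. SAP 7.4 itself plans for rates up to 5%, and the age-0 evaluation is a further defect of the same Diff, not a defence of it.

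**Conclusion.** The SAP is wrong as written: text and code specify different subject and site priors for a must-pass primary safety model, and neither is said to govern. The subject prior can reverse the decision in borderline data with mostly one-eye findings, as with 0.94 against 0.99 in the example. The code is the lenient side. At assumed rates of 2% and 5%, disagreement is about 20% to 23% at latent correlation 0.3 and 11% to 12% at latent 0.7. It is close to zero if 0.70 is a binary correlation, and absent in the low-event cases tried.

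These sizes rest on assumed event rates and on a model without age, sex or baseline findings, and mostly without site. The sensitivity comes mainly from computing rates at zero random effects, which also does not match a hypothesis about proportions of eyes. Severity: should-fix.

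**What to change.** Before database lock:

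1. State one subject prior and one site prior for the slit lamp model, in identical form and on the same scale in SAP 10.1 and SAP 14.1. The prior family is the sponsor's choice.
2. Say whether SAP text or SAP code governs if they differ.
3. At each posterior draw, compute the Test rate, the Control rate and Diff averaged over the site and subject effects and over the observed covariates, including age.
4. For consistency, also align the vision satisfaction site prior, where the code has "PRIOR s2g ~ IGAMMA(.01, s =.01") and SAP 10.1 has 0.001. No effect on that endpoint was calculated.

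The cost is SAP wording and a few lines of code. No data collection, visit or sample size changes. In the worked example, step 3 alone gives the same decision under either prior. Step 1 removes what dependence on the choice of page remains.

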### BEGINNODATA;

P C = logistic(beta0 + 0.5\*beta3); P\_T = logistic(beta0 + beta1 + 0.5\*beta3);

Diff = P T - P C; ENDNODATA; run;

Where, ads SLF =analysis data set for Slit Lamp Findings trtan= numerical representation of treatment, where Test=1 and Control=0 age= Age of subject at time of consent sexn= Numerical representation of sex, where Female=1 and Male=0; siteid= Site Number site\_subjid=Unique Subject ID

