#### Slit Lamp Findings

There were no Grade 3 or higher SLFs observed in any of the historical studies. Assuming no difference between study lenses and a correlation 0.70 between left and right eyes within the same subject (intra-subject correlation), a reference rate of no more than 5% was assumed (worse-case scenario) with a non-inferiority odds ratio margin of 2. A total of 2000 replicating trials were simulated, each replicated sample was analyzed using a generalized estimating equation (GEE) model with a binary distribution and the logit as the link function. Each model included lens type as the only fixed, eye was included as a random effect. The Odds ratio and corresponding 95% confidence interval was used estimate differences between the Test and Control lenses. The upper limit of each 95% confidence interval was compared to 2; if the upper limit was below 2 then NI=1; otherwise NI=0. Statistical power was calculated at the average NI. A sample size of 224 (112 per arm) was chosen to achieve a minimum statistical power of 80%.

Using a reference rate for the control that does not exceed 5% and no more than a 5% difference between the Test and Control lenses translates to an odds ratio margin of 2. A reference rate of 5% was used since this is the worst-case scenario.

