#### **Hypothesis Testing**

The null and alternative hypothesis for Non-inferiority is as follows:

$$\begin{array}{l} H_0 \ p_T - \ p_C \ge 0.05 \\ H_A \ p_T - \ p_C < \ 0.05 \end{array}$$

Where  $p_T$  and  $p_C$  are the proportions of eyes with Grade or higher SLFs for the Test group and Control group, respectively. Non-inferiority will be established if the upper limit of the 2-sided 95% credible interval is below 5%, i.e.  $\Pr(p_T - p_C < 0.05 | y) = 0.975$ .

If the full planned model fails to converge, reduced versions may be considered. In the event that the number of Grade 3 or higher SLFs is too small Grade 2 or higher SLFs will be analyzed and tested as described above.

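### The SAP code judges two primary endpoints on predictions at age 0 and random effect 0, not on the group proportions to which the margins apply

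*SAP*

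**What the plan says.** SAP 10.1 states both hypotheses as differences in proportions. For slit lamp findings, p_T and p_C "are the proportions of eyes with Grade or higher SLFs for the Test group and Control group", with a margin of 0.05. For vision satisfaction in bright lighting they are the proportions of patients who agree or strongly agree, with a margin of -0.1. SAP 4.1 requires all five primary hypotheses to be met.

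The code in SAP 14.1 fits these linear predictors:

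- Slit lamp: "mu = beta0 + beta1*trtan + beta2*age + beta3*sexn + gamma_site + gamma_subject"
- Bright lighting: "mu = beta0 + beta1*TRTAN + beta2*age + beta3*sexn + Gamma_site"

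The blocks that derive the proportions use less. The slit lamp block begins "P C = logistic(beta0 + 0.5" and ends with the sex coefficient; the Test line adds only beta1. The bright-lighting block has "gammac[i] = logistic(theta[i] + beta0 + 0.5*beta3" and a matching Test line. Sex is held at one half. The age term and all random effects are absent.

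Age is defined as age at consent, eligibility is 18 to 49 years, and nothing centres age. For slit lamp findings the text of SAP 10.1 names other covariates: "The regression model will include baseline slit lamp findings and lens type". The code has no baseline findings; it has age and sex instead.

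**The concern.** With an identity link, as for logMAR and CLUE, the omitted terms cancel and the coded difference equals beta1. Lens fit estimates its proportion directly. With a logit link the terms do not cancel: the difference between two probabilities depends on where on the curve it is evaluated. Leaving out beta2*age sets age to 0, outside the data. Leaving out the random effects gives the risk of a subject whose effect is exactly 0. For a rare event with wide variation between subjects, that risk is far below the average risk.

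Two of the five required hypotheses, one of them eye safety, would then be tested on a quantity other than the one hypothesised. Neither omission raises a program error, so nothing would flag it at run time.

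**Working it through.** The plan gives no figure for the coded difference, so there is none to reproduce. The related planning figure, 80% power for slit lamp findings, was not reproduced from the SAP's inputs (22-23% with 112 per arm, correlation 0.70 and odds ratio margin 2). That is a separate matter, and nothing below uses it.

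**Inputs from the documents:** margins 0.05 and -0.1; ages 18-49; slit lamp reference rate 5% and "correlation 0.70 between left and right eyes within the same subject" (SAP 7.4); historical Control satisfaction (51 + 130)/242 = 74.8% (SAP Table 10). **Assumed, because the documents give none:** subject SDs, age slopes, the age distribution and the sex mix.

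**Slit lamp, random effect 0, no age effect.** The group rate is p = ∫ expit(a + s·z) φ(z) dz, where s is the subject SD. Solve for a at p = 0.05 and at p = 0.10; the code reports expit(a). The true difference is 0.05 in every row.

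| Eye correlation at the 5% rate | Subject SD | P_C as coded | P_T as coded | Coded difference |
|---|---|---|---|---|
| 0.10 | 1.29 | 0.0258 | 0.0585 | 0.033 |
| 0.30 | 2.42 | 0.0070 | 0.0210 | 0.014 |
| 0.50 | 3.91 | 0.0008 | 0.0040 | 0.003 |
| 0.70 | 7.0 | 0.000007 | 0.00009 | 0.00009 |

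With Control at 5%, the coded difference reaches 0.05 only at a true Test rate of 15%, 19%, 25%, 32% or 34% for SD 2, 2.77, 4, 6 or 7.

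**Slit lamp, age 0 alone.** Ignoring random effects, the same 10% against 5% gives coded differences of 0.151, 0.085, 0.028 and 0.011 at slopes of -0.05, -0.02, +0.02 and +0.05 log-odds per year.

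**Slit lamp, whole decision.** The model was fitted with age, sex and a subject effect under the SAP priors (site effect omitted, eye correlation 0.70, 50 trials per row, Monte Carlo error up to about 7 points). Percentage of trials declaring non-inferiority:

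| True Control vs Test | As coded | Age centred, random effect still 0 | Group difference |
|---|---|---|---|
| 5% vs 10% | 68 | 100 | 4 |
| 5% vs 15% | 52 | 100 | 0 |
| 5% vs 5% | 86 | 100 | 44 |

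**Slit lamp, zero events.** The data then force beta0 + beta2*age to be very low at ages 18-49, but N(0, 1000) priors leave beta0 alone nearly free. By importance sampling from the priors (116 per arm, no random effects), P(Diff < 0.05) is about 0.86 as coded, short of the required 0.975. It is 1.00 at mean age or with age removed.

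**Grade 2 fallback, true excess 5 points.** The historical rates in SAP Table 9 are 13.5% for Test and 83/270 = 30.7% for Control. At SD 2, 2.77, 4 and 6 the coded differences are 0.034, 0.024, 0.011 and 0.003 from a base rate of 13.5%. From 30.7% they are 0.067, 0.071, 0.069 and 0.051.

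**Bright lighting, age 0.** Take a true difference of -0.10 from 74.8% to 64.8%: logit(0.748) = 1.088 and logit(0.648) = 0.610. At slope -0.04 and an assumed mean age of 33, moving to age 0 adds 0.04 × 33 = 1.32. Then expit(2.408) = 0.917, expit(1.930) = 0.873, and the difference is -0.044. The table averages over ages uniform on 18-49. Its simulation used 112 per arm, 1,000 trials per slope and a normal approximation to the posterior; nominal is 2.5%.

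| Slope per year | Coded difference | False non-inferiority |
|---|---|---|
| -0.06 | -0.025 | 74% |
| -0.04 | -0.044 | 36% |
| -0.02 | -0.071 | 11% |
| 0 | -0.100 | 2.9% |
| +0.03 | -0.120 | 2.0% |

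The covariate-averaged difference gave 2.0-3.1% throughout. Slope -0.06 is a stress case: 89% satisfied at age 18 and 56% at 49. At the SAP's 50% reference rate the age-0 differences are milder: -0.053, -0.077 and -0.097 at -0.06, -0.04 and -0.02, and -0.085 at +0.02. Setting the site effect to 0 matters little: -0.101 to -0.110 for site SDs of 0.2 to 1.0.

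**The case against.** The strongest reply is that SAP 10.1 defines the proportions correctly and nothing ranks the code above the text. On the text's slit lamp covariates there is no age term, so the zero-event failure disappears. In bright lighting, age enters only where judged appropriate. This is fair, but the random-effect-0 fault survives under the text's own model. No wording says how p_T and p_C are obtained from either model, so the code is the only specification.

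Second, the bright-lighting code cannot be used as printed. Its loop reads a fifth element of a four-element theta array, and it monitors an OR that is never defined. It must be rewritten anyway. True, but those faults would probably surface when it is run; the missing age term would not.

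Third, history shows no Grade 3 or higher findings in 860 Test and 270 Control eyes, so 10% against 5% is not the expected result. That stands. The scenario is a type I error check on the margin, and the history points to the zero-event case or to the fallback: "In the event that the number of Grade 3 or higher SLFs is too small Grade 2 or higher SLFs will be analyzed". What counts as too small is undefined, and the fallback is tested in the same way, so it carries the same fault.

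Fourth, direction is mixed and the two slit lamp faults partly offset, as 68% against 100% shows. From the 30.7% Grade 2 base rate the error is conservative. Both points stand, and neither makes the coded quantity the right one.

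**Conclusion.** The concern holds. That the code computes a different quantity from the one hypothesised follows from the printed lines and needs no assumption; only the size does.

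For slit lamp findings random effect 0 is the main fault. At the SAP's planning correlation of 0.70 and no age effect, it turns a true 0.05 into about 0.0001. In the limited simulation on the margin, 68% of trials passed as coded against 4% on the group difference. With no events, the coded age term instead blocks non-inferiority.

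For bright lighting the error is conditional on an age slope: negligible without one, and in either direction with one. Because every primary hypothesis must be met, this must be fixed before the analysis is run.

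**What to change.** Keep the Bayesian logistic and ordinal models and change how the proportions are derived:

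1. At each MCMC draw, compute each subject's or eye's predicted probability under Test and under Control at the observed covariates, integrated over the site effect (and the subject effect for slit lamp). Average over the analysis set, take Test minus Control, and apply the margin to that difference. Say so in SAP 10.1. Centring or dropping age alone does not cure the slit lamp fault.
2. Make the slit lamp code match the SAP 10.1 covariates (baseline findings).
3. Add the difference to both MONITOR lists. For slit lamp it can already be had by subtracting the saved P_C and P_T draws, but it is the wrong difference.
4. In the bright-lighting code, remove the undefined OR and correct the loop bound.
5. State the event count that triggers the Grade 2 fallback.

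The cost is SAP code and wording; no new data are needed.
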